## **5 Study Drug**

### **5.1 Description**

Gabapentin is a GABA analogue anticonvulsant also used to treat neuropathic pain. It is thought to target voltage-gated calcium ion channels at pre- and post-synaptic membranes of neurons in the central and peripheral nervous system modulating the release of neurotransmitters.

Gabapentin is normally available in solid (powder) form and must be compounded into a topical solution. Based on published data of effective topical gabapentin preparation in vulvodynia and experience preparing topical gabapentin for use in patients with pain, IDS Pharmacy of University of Minnesota will compound the gabapentin into the solution for topical use. Once prepared, IDS will also be responsible for dispensing the solution of 6% gabapentin in an appropriate drug container to be given to subjects. Each subject participating in the study will receive enough gabapentin solution for use over four weeks, approximately a maximum of 2 mL a day; 60 mL for 4 weeks. After 4 weeks of treatment (Visit 4) and 8 weeks of treatment (Visit 5) the subject will return for follow up with the prescribed gabapentin container and will be given a new dispensed bottle of the solution for use during the next four weeks.

#### **Treatment Regimen**

Qualified subjects will be educated by the research coordinator on how to properly apply the gabapentin 6% solution two times daily onto intact skin of affected symptomatic scalp areas. The minimum and the maximum size of the scalp areas to be treated will be determined for each subject respectively, based on their disease pattern assessed during Visit 2. Treated sites will be initially recorded and should be treated for the entire 12 weeks unless the skin is adversely affected by the topical gabapentin.

CONFIDENTIAL

This material is the property of the University of Minnesota. Do not disclose or use except as authorized in writing by the study sponsor

Subjects may continue their normal grooming regimen as long as substances without other neuromodulatory agents or steroids are used during the treatment period. Recommended application will be in morning and evening at bedtime. The solution should be applied after hair washing if this coincides with time for application.

## **5.2 Method for Assigning Subjects to Treatment Groups**

All participants will receive treatment with topical 6% gabapentin. The study design does not include a control group, therefore, randomization of participants will not occur.

## **5.3 Preparation and Administration of Study Drug**

IDS will be responsible for the preparation and dispensing of gabapentin 6% solution to the principal investigators or clinical research coordinator (study team). The clinical research coordinator will provide subjects with the solution to administer two times daily after educating them on how to apply the drug. The gabapentin solution should be stored at room temperature (20° to 25°C)/(68° to 77°F) while always properly sealed and away from light and moisture. The study team will provide the subjects with a four week supply of solution at a time. Subjects will contact investigators or coordinator if they need more solution and will be asked to do so promptly if low on solution to avoid gaps in treatment.

## **5.4 Subject Compliance Monitoring**

Subject participants will be informed that they will be asked to stop taking any medications/treatments for their scarring alopecia while participating in this study. This statement will be also written in the consent form that subjects will be asked to read, understand and sign prior participating in the study.

## **5.5 Prior and Concomitant Therapy**

Subjects will be asked detailed information regarding their medical and medication history for general health issues and specific focused questions regarding their symptomatic scarring alopecia.

Subjects will not be allowed to use any medicines/therapies other than the gabapentin 6% solution on the scalp for their symptomatic scarring alopecia.

## **5.6 Packaging**

The gabapentin 6% solution will be prepared through a compounding method by IDS Pharmacy and will be dispensed in red sealed containers with 60 mL of solution.

## **5.7 Blinding of Study Drug**

This is not a blinded study.

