## **2 Study Objectives**

Primary Objective: To assess the role of neurogenic inflammation associated with CGRP expression in scarring alopecia

Secondary Objective: To assess the safety and efficacy of topical 6% gabapentin in subjects with symptomatic scarring alopecia.

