## **3 Study Design**

### **3.1 General Design**

This is a cohort study.

Every subject is expected to schedule 6 visits total to complete the study. The total duration of the study for each volunteer is expected to be approximately 14 weeks.

Prior to gabapentin treatment, there is one visit to screen individuals for participation in the study and to obtain consent. After consent is signed, this visit will also include obtaining history from the subject, clinical evaluation, survey completion, neurometer study, photography, and scalp biopsies. At this initial visit, a total of four 4-mm skin biopsies will be collected. Two biopsies will be collected from affected, symptomatic scalp, and two skin biopsies will be collected from clinically unaffected scalp. Routine histology, confocal microscopy examination, and, if indicated, ELISA CGRP level analysis will be performed on the biopsy specimens. Subjects will start topical 6% gabapentin treatment on Visit 2 (Day 0). Four remaining visits will be scheduled to follow subjects after the start of topical 6% gabapentin treatment. Visits 3, 4 and 5 will occur 4, 8 and 12 weeks respectively after treatment with gabapentin is started. These visits will include labwork to check gabapentin blood levels. During Visit 5, the subject will also be reassessed through clinical evaluation, completion of surveys, neurometer study, photography, and four 4-mm scalp biopsies. Visit 6 will be a follow-up visit two weeks after completion of treatment for suture removal and clinical evaluation of the subject.

CONFIDENTIAL

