### 3.2 Primary Study Endpoints

(1) To assess the role of neurogenic inflammation in symptomatic scarring alopecia and (2) assess the efficacy of topical 6% gabapentin in the management of symptomatic scarring alopecia patients. Subjects' disease burden will be assessed by clinical exam, qualitatively with surveys and neurometer study, and skin biopsies to confirm disease diagnosis, assess disease inflammation, and measure CGRP levels. Subjects will begin topical 6% gabapentin treatment for 12 weeks starting at Visit 2. They will be followed up every 4 weeks during treatment and will be reassessed at week 12 (visit 5) with clinical exam, qualitatively with surveys and neurometer study, and final biopsies to evaluate the impact of gabapentin on the disease and CGRP levels. The surveys to be filled out by the subjects include the Dermatology Life Quality Index (DLQI), Short Form (36) Health Survey (SF-36), Visual Analog Scale for Pain, and Visual Analog Scale for Itch.

CONFIDENTIAL

This material is the property of the University of Minnesota. Do not disclose or use except as authorized in writing by the study sponsor

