#### **6.5 Visit 5 (Week 12)**

The following tests and procedures will be performed:

- Record adverse experiences
- Physical examination of scalp
- Gabapentin blood level
- Review changes in medical history and medications since Visit 4
- LPPAI clinical assessment
- Scalp photography, especially affected areas that are being monitored and treated with gabapentin
- Subject to complete surveys to assess symptomatology: DLQI, SF-36, Pain VAS and Itch VAS
- Neurometer study to assess A $\beta$ , A $\delta$ , and C fiber function after gabapentin administration
- Collect and assess third container of gabapentin solution
- Collect four post-treatment skin biopsy samples: two 4-mm skin biopsy specimens from affected scalp and two 4-mm biopsy specimens from normal-appearing scalp. Specimens will be analyzed for routine histology, confocal microscopic examination, and CGRP level.

Subject has now completed the entire twelve weeks of topical gabapentin therapy.

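### The protocol makes no provision for coded, masked reading of the Visit 1 and Visit 5 biopsies behind its primary CGRP objective, although open treatment does not require it to be open

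*Protocol*

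**What the plan says.** The primary objective in Section 2 is "To assess the role of neurogenic inflammation associated with CGRP expression in scarring alopecia". Section 3.2 gives the tissue its part in the primary endpoints: "skin biopsies to confirm disease diagnosis, assess disease inflammation, and measure CGRP levels", with final biopsies at Week 12 to evaluate the effect of gabapentin on the disease and on CGRP.

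Each subject is biopsied twice. For Visit 1, Section 3.1 says "At this initial visit, a total of four 4-mm skin biopsies will be collected", two from affected and two from clinically unaffected scalp. For Visit 5, Section 6.5 says "Collect four post-treatment skin biopsy samples: two 4-mm skin biopsy specimens from affected scalp and two 4-mm biopsy specimens from normal-appearing scalp". At both visits the instruction is the same: "Specimens will be analyzed for routine histology, confocal microscopic examination, and CGRP level". Section 3.1 makes the ELISA conditional: "Routine histology, confocal microscopy examination, and, if indicated, ELISA CGRP level analysis will be performed on the biopsy specimens".

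On allocation, Section 5.2 says "The study design does not include a control group, therefore, randomization of participants will not occur". On masking, Sections 5.7 and 8.4 both say "This is not a blinded study", with no exception. No section names the specimen reader, or mentions specimen codes, masked reading, reading order or assay batches. The only rule about an assessor is in Section 6.1, which asks that the same person rate a subject's alopecia at each visit. It does not concern tissue.

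**The concern.** Giving the drug openly and reading the tissue openly are separate choices. In a single-arm trial the first cannot be avoided, but the second can: a specimen or stored image can carry a code that hides whether it was taken before or after treatment.

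Confocal and histologic assessment involve judgement, and Section 1.1 tells the reader what to expect, since it reports that gabapentin reduced CGRP in pilot work on normal human tissue. A reader who knows the visit can therefore lean, without intending to, towards lower CGRP or less inflammation at Visit 5. With no concurrent arm read in the same way, nothing in the data separates that lean from a drug effect. It would affect a descriptive summary as much as a formal test, and no later analysis can remove it.

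**Working it through.** **Inputs from the protocol.** 10 subjects (Section 7.1); 4 biopsies at Visit 1 and 4 at Visit 5, half from affected scalp each time (Sections 3.1, 6.1, 6.5); Visit 1 at Day -14 and Visit 5 at Week 12 (Table 1). Section 7.1 gives no significance level, power, effect size or standard deviation, and Section 7.2 names no test. There is thus no stated calculation to reproduce.

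**Specimens to code.** 10 × (4 + 4) = 80, of which 10 × 2 × 2 = 40 are affected and 40 unaffected, half of each at each visit. This is a maximum, because withdrawn subjects are not replaced (Section 4.4.2).

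**Time between the two sets.** 2 weeks + 12 weeks = 14 weeks.

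**Exposure of each reading.**
- Confocal microscopy and histology: judgement is involved, so reader expectation is the main risk.
- ELISA CGRP: an instrument reading, done only in some circumstances under Section 3.1. The risk here is a shift between assay runs if the two visits are run apart. The protocol does not say when assays are run.
- Before/after contrast: exposed to both risks.
- Affected/unaffected contrast within one visit: exposed to reader expectation, but a shift between runs need not touch it.

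**Illustration of susceptibility (assumed inputs).** Let *p* be the chance that a subject's Visit 5 reading is scored lower than the Visit 1 reading when nothing has changed; *p* = 0.5 is an unbiased reader. The chance that at least *r* of 10 subjects appear to fall is

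P(X ≥ r) = Σ from k = r to 10 of C(10,k) p^k (1 − p)^(10 − k).

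At *p* = 0.5 and *r* = 9 this is (10 + 1)/1024 = 0.0107. At *p* = 0.7 it is 10 × 0.7^9 × 0.3 + 0.7^10 = 0.1211 + 0.0282 = 0.1493.

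| p (assumed) | at least 8 of 10 lower | at least 9 of 10 lower |
|---|---|---|
| 0.5 | 0.0547 | 0.0107 |
| 0.6 | 0.1673 | 0.0464 |
| 0.7 | 0.3828 | 0.1493 |
| 0.8 | 0.6778 | 0.3758 |

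The values of *p* above 0.5 are assumptions. The table shows how easily a modest lean could look like a consistent response in 10 subjects. It does not predict what will happen in this trial.

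**The case against.** The strongest reply is that the sentence on blinding stands under headings about study drug and unblinding, where it is correct. The protocol nowhere says what the specimen reader sees, and a laboratory procedure or analysis plan not at hand may already require coded reading and common batches. This stands in part. A reader might infer that the protocol plans to have biopsies read with visit and site known. It does not say so, and the supportable statement is that it makes no provision for masking. But coding and storage have to be settled before the first biopsy, so this is not something an analysis plan can supply later. The protocol does set an assessor rule for the clinical rating and has no counterpart for the tissue behind its primary objective.

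A second temptation is to quote a false-positive rate. With a two-sided paired t-test at n = 10, an assumed bias of 0.3 to 0.5 standard deviations of the paired change would give nominal significance in about 14% to 29% of trials with no true effect, instead of 5%. The documents do not support using this as a property of the study: Section 7.2 plans descriptive summaries of symptom and sign scores, names no test, and nothing in the protocol indicates a bias of that size.

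Three practical limits also stand. Scarring may reveal affected tissue, so site can be masked only in part. Visit 1 histology serves diagnosis and needs an early identified reading, so the same person might recognise the material later. And holding specimens for about 14 weeks assumes that they keep, which the protocol does not address.

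**Conclusion.** The point holds as a gap that is cheap to close, and not as a finding that open reading is planned. The tissue readings carry the primary objective, the design has no control group, the expected direction under treatment is stated in advance, and nothing protects the confocal and histologic readings from that expectation. For ELISA the concern is narrower: possible drift between runs, if the two visits are assayed apart.

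The size of any bias cannot be derived from the documents. What can be said is that up to 80 specimens are affected and that, with 10 subjects, a modest lean is enough to imitate a consistent fall. The conclusion assumes that no other study document already requires masked reading. If one does, a sentence in the protocol referring to it settles the matter.

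**What to change.** Keep the statement that treatment is open, and add to Section 5.7, with a reference from Sections 6.1 and 6.5, that:

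- research specimens and stored confocal images are coded so that whoever reads them does not know the visit and, as far as the tissue allows, the site;
- coded material is read in mixed order after Visit 5, and the code is opened only once the readings are recorded;
- diagnostic histology at Visit 1 is still read at once, and any histologic score used for the research comparison comes from a later coded reading;
- where specimen stability allows, each subject's Visit 1 and Visit 5 CGRP assays are run in the same batch.

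Confocal photographs are already kept as source data (Section 9.2), so coded image reading needs no new procedure. Coding the specimen itself is better where possible, because choosing which field to photograph is also a judgement.

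The cost is label coding, someone to hold the code, storage until Visit 5, and later research results. It needs no additional subjects, arm or biopsies. Two things should be checked first: that the specimens tolerate storage, and that deferral does not disturb whatever triggers the conditional ELISA in Section 3.1.

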## **5.8 Receiving, Storage, Dispensing and Return**

CONFIDENTIAL

### **5.8.1 Receipt of Drug Supplies**

The Department of Dermatology Clinical Research Division will order 10 initial containers of 60 mL solution of gabapentin 6% solution from the IDS Pharmacy, University of Minnesota, Mayo Building, 2nd floor.

Upon receipt of the study treatment supplies, an inventory will be performed and a drug receipt log filled out and signed by the person accepting the shipment. It is important that the designated study staff counts and verifies that the shipment contains all the items noted in the shipment inventory. Any damaged or unusable study drug in a given shipment will be documented in the study files.

Prepared containers of gabapentin solution 6% will be kept at room temperature (20° to 25°C) away from moisture and light for up to 24 months at the IDS pharmacy, University of Minnesota, Phillips Wangensteen Building, 2nd floor.

### **5.8.2 Dispensing of Study Drug**

IDS will dispense the drug-filled container to the investigators or coordinators. Once qualified to begin treatment, each subject will receive one container of 60 mL of gabapentin 6% solution from the clinical coordinator. Regular study drug reconciliation will be performed to document drug assigned. During follow-up visits, drug consumed and drug remaining will be recorded. This reconciliation will be logged on the drug reconciliation form, and signed and dated by the study team.

### **5.8.3 Return or Destruction of Study Drug**

At the completion of the study, there will be a final reconciliation of drug dispensed, drug consumed, and drug remaining. This reconciliation will be logged on the drug reconciliation form, signed and dated. Any discrepancies noted will be investigated, resolved, and documented prior to return or destruction of unused study drug. Drug destroyed on site will be documented in the study files.

## **6 Study Procedures**

### **6.1 Visit 1 (Screening/baseline)**

Before any study-related procedures are performed, subjects will be screened for participation in the study using inclusion and exclusion criteria. Once determined to be a qualified candidate for participation, subjects will be asked to read and sign the consent form if they wish to participate in this research study. They will then be asked about their medical and medication history.

The following tests and procedures will be performed:

- Obtain medical history and medications
- Physical examination of scalp
- Lichen Planopilaris Activity Index (LPPAI) clinical assessment will be performed. Every effort will be made to have the same person evaluate the alopecia at each visit for any given subject.

CONFIDENTIAL

- Scalp photography, especially affected areas that will be monitored and treated with gabapentin
- Subject to complete surveys to assess symptomatology pre-treatment: DLQI, SF-36, Pain VAS and Itch VAS
- Neurometer study to assess A $\beta$ , A $\delta$ , and C fiber function before gabapentin administration
- Collect four pre-treatment skin biopsy samples: two 4-mm biopsy specimens from affected scalp and two 4-mm biopsy specimens from normal-appearing scalp. Specimens will be analyzed for routine histology, confocal microscopic examination, and CGRP level.

If potential symptomatic subjects are currently taking medications/treatments for their scarring alopecia, they will be asked to stop the treatment as noted in the exclusion criteria in section 4.2.

## **6.2 Visit 2 (Day 0)**

The following tests and procedures will be performed:

- Record adverse experiences
- Biopsy suture removal
- Review changes in medical history and medications since Visit 1
- LPPAI clinical assessment
- Scalp photography, especially affected areas that will be monitored and treated with gabapentin
- Subject to complete surveys to assess symptomatology pre-treatment: DLQI, SF-36, Pain VAS and Itch VAS
- Educate subject on how to apply topical gabapentin solution
- Provide subject with first container of gabapentin solution
- Subject begins treatment with topical gabapentin solution

## **6.3 Visit 3 (Week 4)**

The following tests and procedures will be performed:

- Record adverse experiences
- Gabapentin blood level
- Review changes in medical history and medications since Visit 2
- LPPAI clinical assessment
- Subject to complete surveys to assess symptomatology: DLQI, SF-36, Pain VAS and Itch VAS
- Collect and assess first container of gabapentin solution
- Provide subject with new container of gabapentin solution

Subject has now completed four weeks of topical gabapentin therapy. Answer any questions/concerns subject has about drug application and collect feedback on ease of use and/or impact on grooming practices.

CONFIDENTIAL

#### **6.4 Visit 4 (Week 8)**

The following tests and procedures will be performed:

- Record adverse experiences
- Gabapentin blood level
- Review changes in medical history and medications since Visit 3
- LPPAI clinical assessment
- Subject to complete surveys to assess symptomatology: DLQI, SF-36, Pain VAS and Itch VAS
- Collect and assess second container of gabapentin solution
- Provide subject with new container of gabapentin solution

Subject has now completed eight weeks of topical gabapentin therapy. Answer any questions/concerns subject has about drug application and collect feedback on ease of use and/or impacting on grooming practices.

#### **6.5 Visit 5 (Week 12)**

The following tests and procedures will be performed:

- Record adverse experiences
- Physical examination of scalp
- Gabapentin blood level
- Review changes in medical history and medications since Visit 4
- LPPAI clinical assessment
- Scalp photography, especially affected areas that are being monitored and treated with gabapentin
- Subject to complete surveys to assess symptomatology: DLQI, SF-36, Pain VAS and Itch VAS
- Neurometer study to assess A $\beta$ , A $\delta$ , and C fiber function after gabapentin administration
- Collect and assess third container of gabapentin solution
- Collect four post-treatment skin biopsy samples: two 4-mm skin biopsy specimens from affected scalp and two 4-mm biopsy specimens from normal-appearing scalp. Specimens will be analyzed for routine histology, confocal microscopic examination, and CGRP level.

Subject has now completed the entire twelve weeks of topical gabapentin therapy.

#### **6.6 Visit 6 (2 week follow-up)**

The following tests and procedures will be performed:

- Record adverse experiences
- Review changes in medical history and medications since Visit 5
- LPPAI clinical assessment
- Subject to complete surveys to assess symptomatology: DLQI, SF-36, Pain VAS and Itch VAS
- Biopsy suture removal

CONFIDENTIAL

A flowchart of the study can be found in Section 3.1 General Design.

## 7 Statistical Plan

### 7.1 *Sample Size Determination*

This is a pilot study with the plan to enroll 10 subjects. The reasoning for sample size selection is to proceed with preliminary studies in a small group. All subjects will be selected based on inclusion and exclusion criteria.

### 7.2 *Statistical Methods*

An intent-to-treat analysis will be performed in all subjects for symptoms and sign scores comparing the last treatment visit to baseline. A combination of methods will be included for analysis. Descriptive statistics including either numerically or graphical representations to summarize the data will be used.

